5.4.1 Early Call Triggers (Up to 3 Months)

The research coordinator will alert the designated site clinician and appropriate study team members when a patient reports to the coordinator any of the following symptoms:

- 1. Persistent fevers or chills;
- 2. Persistent vomiting and/or inability to take medication;
- 3. Worsening abdominal pain despite pain medication;
- 4. Patient requesting discussion with medical team; and
- 5. Clinical concern by research coordinator (e.g., significant persistent dizziness or significant new diarrhea).

The designated site clinician and study team will be responsible for determining if further evaluation is needed and for coordinating the patient's care upon receiving notification from the research coordinator. The research coordinator will document contact with the study team by either 1) responding to the Survey Response Review report on the CODA portal if report of the call trigger was in response to a triggered surveyed question or 2) documenting by way of an internal study team call trigger tracking system concerns that are spontaneously reported.

The site RC will be responsible for initiating the Serious Adverse Event (SAE) reporting process if the reported patient concern is an SAE. See Section 9.0.

5.4.2 Late Call Triggers (Beyond 3 Months)

Despite a requirement that all patients enrolled in the study have diagnostic imaging of the abdomen to exclude the possibility of a cancer, it is still possible that patients treated with antibiotics only may harbor an appendiceal mass. The research coordinator will alert the designated site clinician and study team if any of the following are reported any time after three months:

- 1. Complaints of signs and symptoms of recurrent appendicitis;
- 2. Unintentional weight loss of more than 15lbs; or
- 3. Diagnostic imaging consistent with appendiceal mass.

If the patient has not seen a healthcare provider to address these issues, the research coordinator will offer to connect the patient to the appropriate scheduling coordinator to make an appointment for follow-up at any of the clinical sites or the lead of the CCC.

As noted in Section 5.4.1, the research coordinator will document contacting the study team by either 1) responding to the Survey Response Review report on the CODA portal if report of the

call trigger was in response to a triggered surveyed question or 2) documenting by way of an internal study team call trigger tracking system concerns that are spontaneously reported.

Additionally, the site RC will be responsible for initiating the SAE reporting process if the reported patient concern is an SAE. See Section 9.0.

5.4.3 Clinician Education

Clinicians will be advised to follow usual clinical care pathways and principles in responding to these call triggers described in Sections 5.4.1 and 5.4.2. Additionally, site clinical leads will be formally educated through training sessions on the following study materials: protocol, research coordinator call triggers, and SAE reporting process.

Clinicians will be encouraged to apply usual clinical care and potentially, repeat diagnostic imaging or colonoscopy for participants who did not have an appendectomy and have persistent gastrointestinal symptoms at or after one-year.

5.5 Reasons for Withdrawal

Participants may be withdrawn from the study for the following reasons:

- 1. Participant desires withdrawal (reasons for withdrawal will be recorded); and
- 2. Study investigator(s) deems it in the participant's best interest to be withdrawn (reason for withdrawal recorded).

5.5.1 Handling of Withdrawals

If the participant requests to be withdrawn from the study, they will be given appropriate treatment, but will not continue with scheduled study follow-ups. If the participant withdraws from the study and withdraws consent for disclosure of future information, no further evaluations will be performed and additional data will not be collected. The investigators may retain and continue to use data collected before withdrawal of consent.

5.6 Compensation

5.6.1 Participant Compensation

Participants will be paid up to \$155 for completing the research assessments described in Table 2 (Section 5.0). Payment will be provided on a pro-rated, weighted fashion: \$20 for the Baseline Assessment, \$10 for the Week 1 and 2 Assessments (\$20), \$20 for the Week 4 Assessment, \$10 for Quarterly Assessments through 12 months (\$40, Months 3, 6, 9, 12), \$10 for the 18-month Assessment, and \$15 for the 24-month Assessment. Extended follow-up surveys at 36, 48, and 60 months will also be pro-rated at \$10 per survey. Compensation will be distributed to participants centrally by UW research staff unless other arrangements have been made.

5.6.2 Site and Site Lead Compensation

Each site will determine how best to allocate their funds to support this research at their hospital. Funds may be used to support study staff including site surgical and ED lead investigators, relevant clinical and research support staff, and research study supplies. Funds

for research participant compensation will not come directly from these site payments but rather provided by UW centrally as described in Section 5.6.1.

5.7 Retention Activities

5.7.1 Maintaining Contact

Participants will be asked to confirm their contact information before beginning each research assessment. They will also be asked to confirm the contact information of family members, friends, and employers who may be asked to update the participant's contact information should they be otherwise lost to follow-up. Participants may receive personalized birthday cards with \$5.00 coffee-shop gift card or other small incentive annually during their birthday month.

5.7.2 Contact between Assessments

Three interim communications will be performed between 12 and 24 month follow-up assessments to help retain participants in the study and to improve communication with them. During the year, coordinators will:

- 1. Send a thank-you "mailer" to the participant in recognition of his or her participation. The mailer may include an updated site newsletter and a small token of appreciation, such as a pen with the study logo;
- 2. Request an update in contact information; and
- 3. May send a birthday card with a \$5 gift card or another small incentive.

6.0 Outcome Assessments

6.1 Primary Outcome

Patient Reported Outcomes (PROs) will be assessed for adults using both generic and diseasespecific surveys utilizing the QoL instruments in Table 4.

Table 4. PRO Measures.

Validated Scale	Description
EQ-5D ²⁰	A preference-based instrument designed to measure generic health status across 5 dimensions of health: mobility, self-care, usual activities, pain/discomfort, and anxiety/depression, with 3 response levels (i.e., no problems, some problems, extreme problems). A Visual Analog Scale (scored 0-100) is also included.
10 PROMIS Global Health Short Form ²¹	A 10-item instrument measuring domains that can be scored into a Global Physical Health component and Global Mental Health component. Each item includes 5 response choices, with the exception of the common 11-point pain intensity item ("How would you rate your pain on average?" with 0=no pain and 10=worst imaginable pain).
Decision Regret Scale ²³	A 5-item validated questionnaire that measures regret among patients following a specific treatment decision. Scores range from 0-100 and higher scores reflect higher levels of regret. While developed for use in patients undergoing treatment for cancer, the questions are general in nature and adaptable to diverse clinical experiences.
GIQLI ²²	A 36-item questionnaire assessing 5 domains: GI symptoms, physical function, emotional well-being, social well-being and perception of medical treatment measured by a single item question. Each item has 5 response choices (i.e., all of the time, most of the time, some of the time, a little of the time, never). In addition, the measure produces and overall QoLscore (0-144) where higher numbers indicate greater QoL.

6.2 Secondary Outcomes

6.2.1 Clinical Complications

Death, SAEs, and complications (reported as AEs via EMR review) will be assessed and recorded through the study surveillance period. Complications (reported as AEs) will incorporate NSQIP standards and definitions as well as events related to antibiotic-related complications.

Serious Adverse Events	Adverse event
Death	
Life-threatening event	
Severe antibiotic reaction	Mild/moderate antibiotic reaction
CVA or stroke	
MI requiring treatment or cardiac arrest	Myocardial infarction Atrial arrhythmia
Unplanned admit to ICU	
Acute Renal Failure (requiring dialysis)	Major UTI (e.g., pyelonephritis) Urinary retention Acute Renal Failure (no dialysis) Progressive renal insufficiency
C. difficile colitis (requiring colon resection)	
Pulmonary embolism requiring therapy	DVT/PE requiring treatment
Coma >24 hours	
Septic shock (requiring pressors)	Sepsis
Serious Adverse Events (continued)	Adverse event (continued)
Bleeding requiring transfusion	
Newly infected prosthetic graft infection	
(such as a cardiac valve that gets infected or	
synthetic bypass graft infection secondary to	
appendicitis)	
Mechanical ventilation >48 hours	Tracheal reintubation/tracheostomy
Colostomy or ileostomy	NG tube replacement (non-routine)
	Bowel obstruction
	Ileus
	Organ/space infection (including peritonitis)
	Surgical site infection
	Intra-ab Abscess
	Severe dehydration
	Hernia
	Malignant hyperthermia
	Pneumonia
	Other infection
	Other post-op occurrence: unspecified
	Other non-operative intervention: unspecified
	Unplanned (re)operative intervention during index
Other life threatening count	C. difficile colitis (not requiring colon resect)
Other life threatening event	
Rehospitalization (other than for txt of appendicitis)	

Monitored event
Appendiceal cancer
Perforation
Length of stay postoperatively

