Inspired by the antibiotics-only approach results between 1956 and 2015, and with advances in radiologic imaging to diagnose and stage the progression of disease, there were six randomized trials comparing antibiotics to appendectomy among patients with AUA. These trials, all performed in Europe. 6-11 found that nearly 3 out of 4 patients in the antibiotics treatment group avoided surgery in the first year after diagnosis. A meta-analysis of five of these studies (the most recent published in 2015) found that antibiotic treatment was associated with a 46% reduction in complications and less pain and disability than routine appendectomy. 12 No participant deaths occurred in the trials, and the rates of perforation were lower among those in the antibiotic treatment group. However, existing trials suffer from important limitations. These include small sample sizes leading to indeterminate results, lack of imaging leading to potential inclusion of patients with complicated appendicitis and potentially without appendicitis at all, inexact and treatment dependent outcome definitions (rate of appendectomy) and operation/reoperation criteria, arbitrarily prolonged hospitalization, limited use of laparoscopic techniques. inadequate antibiotic regimen activity, and short-term follow-up (no studies followed patients beyond one year). Furthermore, none of these trials included keeping a record of the patient's experience with treatment in a standardized fashion. Perhaps as a result of these evidence gaps, nearly all United States (U.S.) patients with appendicitis (97.5% according to a recent California [CA]-based administrative database analysis¹³ and similar findings in Washington [WA] [personal communication [name]]) undergo appendectomy. Conversely, in Europe where the trials originated, it now appears that 1 in 5 patients with AUA are being offered the antibiotics approach.

It remains to be determined whether patient experience with the antibiotics strategy (performing appendectomy only when the patient gets worse on antibiotics or has a recurrence of disease) is "just as good as" appendectomy. This comparison should consider the overall impact of the treatment on their health, well-being, quality of life (QoL), healthcare burden, and all clinical endpoints (e.g., resolution of symptoms, need for eventual appendectomy, complications). It also remains to be determined what patient and clinical factors are associated with worse outcomes.

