1. Safety Monitoring – We will perform interim analyses of accruing safety data. SAEs (described in section 9.1) will be monitored throughout the course of the study. The DSMB will review tabulated SAEs by treatment group every six months; however, all deaths will be reported to the DSMB immediately. With additional guidance from the DSMB, we propose to monitor and compare three safety endpoints between randomization groups: 1) per-patient indicator of "any" SAE, 2) per-patient SAE count, and 3) all-cause mortality. The research coordinators at each practice site will monitor participants for, or be alerted by UW study staff regarding the presence of, SAEs and AEs during inpatient stays using EMR. This process includes reviews of SAEs and AEs that occur at other hospitals not included in the study, with details obtained through requested records from those hospitalizations. An adjudication process related to these events will be led by a clinician not otherwise involved in the trial. This independent safety monitor (ISM) will review SAE forms for data quality control. SAE forms needing additional specification will be returned to the site PI for completion prior to finalization. All SAEs will also be adjudicated by the surgical site lead.

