Based on data from prior studies, we anticipate that SAEs in the ITT antibiotics arm will be less common than in the appendectomy arm. Since appendectomy is considered standard of care and it is desirable to assess effectiveness within subgroups, we do not propose formal statistical stopping rules if SAE rates are lower in the antibiotics arm. However, evidence of higher SAEs in the antibiotics arm will require DSMB consideration of the trial's continuation. At the planned interim analysis, we will use onesided tests to formally compare the event rates across the two ITT treatment groups using appropriate small sample methods such as Fisher's exact test or Poisson regression with robust standard errors for SAE per-patient counts. We will also monitor and compare the rates of SAEs in the appendectomy arm to the rate of SAEs among patients in the observational cohort who receive appendectomy to address concerns that surgery following antibiotic therapy may be associated with a higher surgical risk. For safety monitoring we will utilize a one-sided Pocock stopping boundary^{38,39} (α =0.025) where, at the discretion of the DSMB and faculty statistician, study recruitment may be discontinued if there is substantial statistical evidence for a higher safety event rate in the antibiotics arm compared to the appendectomy arm (P<0.011 at either interim or final analysis). In other words, the DSMB will consider stopping the trial on the basis of safety if there is substantial statistical evidence that patients randomized to the antibiotics treatment are experiencing a higher rate of SAEs than patients randomized to appendectomy.

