9.2 SAE Reporting

Life-threatening complications or SAEs are a very rare possibility with surgical treatment and even less likely with antibiotic treatment. SAEs are defined as one of the following conditions (also listed in section 6.2.1):

- 1. Death during the period of protocol-defined surveillance;
- 2. Life-threatening event related to the treatment or significant disability/incapacity related to the treatment; or
- 3. Inpatient hospitalization (other than for treatment of recurrent appendicitis).

All SAEs will be:

- 1. Recorded on the appropriate SAE case report form;
- 2. Adjudicated by the ISM;
- 3. Reviewed and evaluated by the DSMB;
- 4. Followed until satisfactory resolution or until the study investigators deem the event to be chronic or the participant to be stable;
- 5. Reported to the study investigators, the project managers, and site IRBs per their reporting guidelines; and
- 6. The study investigators will also report SAEs to PCORI in its role as funder.

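### Sections 6.2.1 and 9.2 exempt different appendicitis admissions from the SAE definition, so a complicated readmission counts after surgery but may not after antibiotics, and the safety stopping test can lean towards antibiotics

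*Protocol*

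**What the plan says.** Protocol 6.2.1 lists as an SAE "Rehospitalization (other than for txt of appendicitis". Protocol 9.2 lists "Inpatient hospitalization (other than for treatment of recurrent appendicitis" and says that its conditions also appear in 6.2.1. The first exempts readmission for any appendicitis, the second only for recurrent appendicitis.

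In the 6.2.1 table "Intra-ab Abscess" stands in the adverse-event column, as do organ/space infection (including peritonitis), ileus and sepsis. Only septic shock needing pressors is in the serious column. Perforation is a monitored event.

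Section 8.6 item 1 proposes three safety endpoints: an indicator of any SAE, "2) per-patient SAE count, and 3) all-cause mortality". One-sided tests are to "formally compare the event rates across the two ITT treatment groups", with a Pocock boundary of P<0.011 at each look. The rule acts in one direction: "study recruitment may be discontinued if there is substantial statistical evidence for a higher safety event rate in the antibiotics arm". Whether to act on it is left to the DSMB and the statistician. Section 8.6 also says that interim monitoring concentrates on events in the first four weeks.

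**The concern.** The stopping rule acts in one direction: it looks for more serious harm on antibiotics. A patient whose appendix has been removed can hardly be readmitted for appendicitis, so the exemption works almost entirely in the antibiotics arm. (Appendectomy-arm patients who refuse surgery stay in that arm under ITT and could also fall under it.)

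An abscess or organ/space infection is not an SAE in itself and becomes one mainly through readmission. After surgery that route is open. After antibiotics the same readmission may be labelled treatment of appendicitis and drop out. Neither section says how to class it. At stake is whether two of the three monitored safety endpoints compare like with like. Section 2.0 itself faults earlier trials for outcome definitions that depended on treatment.

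**Working it through.** **1. The boundary.** With three equally spaced looks and overall one-sided alpha 0.025, solve P(any Z_k > c) = 0.025 with corr(Z_i, Z_j) = √(t_i/t_j). This gives c = 2.289 and nominal p = 0.01103, which matches the plan's 0.011. At looks of 400, 900 and 1552 patients, using 0.011 gives an overall alpha of 0.026. The boundary is sound. The question is what is counted.

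**2. The two wordings side by side.**

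| Event | Appendix removed | Antibiotics, 6.2.1 | Antibiotics, 9.2 |
|---|---|---|---|
| Readmission with abscess, organ/space infection or sepsis without shock | SAE | Exempt if labelled treatment of appendicitis | SAE unless labelled recurrent |
| Early readmission for failed initial treatment, no complication | Does not arise | Exempt | SAE, if not regarded as recurrent |
| Later uncomplicated recurrence | Does not arise | Exempt | Exempt |
| Death, septic shock, ICU admission | SAE | SAE | SAE |

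The documents do not settle which wording governs. Section 8.6 item 1 sends the reader to 9.1. That section covers identification only, the definition is in 9.2, and 9.2 points back to 6.2.1. Section 4.5.2 speaks of recurrence after the four-week assessment. The final SAP (Exploratory Aim A) places it after symptom resolution, 30 or more days from randomization. On those descriptions an early failure is not recurrent, so it is an SAE under 9.2 but exempt under 6.2.1.

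**3. Same complication rate, counted in one arm only.** The documents give no SAE or readmission rates, so all rates below are assumptions. Let o_A and o_C be the other-SAE rates, a the abscess readmission rate (equal in both arms, in different patients from the other SAEs), and f the share counted in the antibiotics arm.

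p_A = o_A + f·a; p_C = o_C + a

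Chance of crossing = Σ Bin(x; n, p_A)·Bin(y; n, p_C) over all (x, y) with one-sided Fisher P<0.011.

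Take o_A = 5%, o_C = 2% and n = 776 per arm (1552/2), at a single look:

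| a | Counted in both arms (f = 1) | Counted only after surgery (f = 0) |
|---|---|---|
| 2% | 7% v 4%: 58% | 5% v 4%: 7% |
| 1% | 6% v 3%: 68% | 5% v 3%: 35% |

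Simulating all three looks (200, 450 and 776 per arm; 20,000 trials) gives 62% to 10% for a = 2% and 71% to 39% for a = 1%. If half the antibiotics-arm abscess readmissions are counted at a = 2% (6% v 4%), the three-look figure is 32%.

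**4. Excess complicated readmissions on antibiotics.** Assume other SAEs at 3% in each arm and an extra 1 to 2.5 points of complicated readmissions in the antibiotics arm. This would be 20% to 50% of an assumed 5% appendicitis readmission rate.

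| Per arm | Not counted (3% v 3%) | +1 point (4% v 3%) | +2.5 points (5.5% v 3%) |
|---|---|---|---|
| 200 | 0.6% | 2.3% | 10% |
| 450 | 0.7% | 5.1% | 28% |

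These figures are for the Fisher test of any SAE. The Poisson test of SAE counts uses the same events and was not calculated.

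**The case against.** The strongest reply is that 9.2 governs monitoring. Early failures then count as SAEs in the four-week window, and the tilt there could be close to nil. That is a fair reading and it limits the claim. But 9.2 says it matches 6.2.1, which it does not, and a site following 6.2.1 would classify the event differently.

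Second, appendectomy after failure or recurrence is part of the randomised strategy, and 8.6 items 3 and 4 decline any stopping rule on failure rates. A reader might therefore treat every exempt appendicitis readmission as lost harm and obtain very large crossing probabilities. The documents do not support that: counting all of them would bring back, indirectly, a rule the plan rejects. Only complicated readmissions are at issue. A reader might also take the statement that "nearly 3 out of 4 patients in the antibiotics treatment group avoided surgery in the first year after diagnosis" to mean that a quarter of the antibiotics arm is exempt. That figure is one-year surgery in earlier trials and may include operations during the index stay. It says nothing about readmission within four weeks.

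Third, there are safeguards. Mortality is unaffected and the listed life-threatening events count in both arms. An independent safety monitor reviews SAE forms, and stopping is discretionary. The final SAP compares appendicitis-related events, including perforation and drainage procedures, between ITT arms under Aim 2. All of this stands and softens the point. However, Aim 2 does not feed the stopping test, and no rule tells a site when an appendicitis readmission needs an SAE form.

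**Conclusion.** The point holds as an inconsistency between two SAE definitions and an undefined boundary that works differently by arm. If the exemption is applied to complicated readmissions, the any-SAE and SAE-count comparisons shift towards antibiotics; that direction does not depend on the assumed rates. The size does, and the documents give none. In the illustrations, counting the complication only after surgery cuts the chance of crossing by about half (abscess 1%) to nearly nine tenths (abscess 2%). Counting a modest excess of complicated readmissions raises it to between 2% and 28%.

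A reader might infer that the plan writes abscess after antibiotics out of the SAE count. It does not say so; that classification is left open. Nor do the documents show that exempt events would make up most of the antibiotics arm's events. This should be corrected, but it does not undermine the primary EQ-5D analysis.

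**What to change.** 1. Reconcile 6.2.1 and 9.2 so that a single definition feeds the safety endpoints in 8.6, and correct the cross-reference from 8.6 item 1.
2. For the between-arm safety endpoints only, count a readmission with a complication listed in 6.2.1 (abscess, organ/space infection, sepsis and so on) as an event in both arms, whether or not it is also labelled treatment of appendicitis. Uncomplicated recurrence stays exempt and the SAE form is unchanged.
3. Report perforation separately and do not use it as a trigger. At readmission it can occur almost only while the appendix remains, so using it would create the opposite asymmetry.
4. Add one supportive row, with no stopping rule attached, to the DSMB and Aim 2 tables: any unplanned rehospitalization including appendicitis, by randomised arm, over the same window. The DSMB table shells are in an appendix that is not in the text available here, so first check whether such a row exists.

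The cost is a small derivation from forms already listed in 5.3. Section 8.6 allows the monitoring guidelines to be revised on DSMB recommendation. The drawback is a less favourable antibiotics-arm event rate, which the DSMB will have to read with expected recurrence in mind.
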